4.2.4. Summary of Studies in Adults

In single- and multiple-dose Phase 1 studies in adults, the Cmax and AUC of ceftaroline increased approximately in proportion to increases in dose within the dose range of 50 to 1000 mg, and no accumulation of ceftaroline fosamil or active ceftaroline was observed with either q12h or every 24-hour multiple dose regimens. Ceftaroline Cmax was generally reached near the end of the IV infusion, and the terminal elimination half-life (T½) of ceftaroline was typically in the range of 2.0 to 2.6 hours. Following IV infusion of [14C] ceftaroline fosamil, 87.5% of the dose of radioactivity was excreted in urine and 6.0% was excreted in feces, confirming that urinary excretion is the principal route of elimination. A significant percentage of the ceftaroline fosamil dose was excreted in the urine as ceftaroline (approximately 40% to 70%). No dosage adjustment is considered necessary for subjects with mild renal impairment. Dosage adjustment is recommended in subjects with moderate and severe renal impairment (creatinine clearance [CrCl] ≤ 50 mL/min).

Study CEF-PK-02 was a recently completed Phase 1, open-label, multiple-dose study in healthy adult subjects to assess the concentration of ceftaroline in ELF. Subjects were randomized to receive one of the following dosing regimens: Treatment A - 600 mg ceftaroline fosamil q12h for 3 days with a single dose on Day 4; Treatment B - 600 mg ceftaroline fosamil every 8 hours (q8h) for 3 days with a single dose on Day 4. Twenty-five subjects received each dosing regimen. Plasma samples for PK analysis were collected pre dose and over 24 hours after the final dose on Day 4. Subjects underwent bronchoscopy and BAL at a single time point after the last dose in order to collect ELF. Preliminary data indicate that the ratio of AUCs of free ceftaroline in ELF to free ceftaroline in plasma, assuming 20% protein binding in plasma and no protein binding in ELF, was approximately 22%. All subjects had measurable ceftaroline concentrations in ELF at 1, 2, 4, and 6 hours after the start of the ceftaroline fosamil infusion. Eight out of 10 subjects that underwent BAL 8 hours after dosing had measurable ceftaroline concentration in ELF, and none of the 5 subjects that underwent BAL at 12 hours after dosing had measurable ceftaroline in ELF. These data demonstrate that ceftaroline is able to penetrate into ELF and concentrations of ceftaroline in ELF appreciably exceeded the MIC90 for ceftaroline against *S. aureus* (1 mg/L) at 1 and 2 hours after the start of the ceftaroline fosamil infusion in all subjects. Plasma and ELF concentrations were similar for the 2 dosing regimens, with the q8h regimen showing slightly (approximately 15% to 20%) higher concentrations on average. Ceftaroline appeared to be eliminated from plasma and ELF at a similar rate.

Ceftaroline fosamil at a dose of 600 mg (or 400 mg if the subject had renal impairment) q12h was well tolerated in 693 adult subjects in the 2 completed Phase 3 CAP studies. As shown in these studies,

monotherapy with ceftaroline fosamil at a dose of 600 mg administered as a 1-hour IV infusion q12h for 5 to 7 days is effective for the treatment of CABP caused by susceptible isolates of the following gram- positive and gram-negative microorganisms: *S. pneumoniae* (including cases with concurrent bacteremia), MSSA, *H. influenzae*, *K. pneumoniae*, *K. oxytoca*, and *E. coli*.

Therapy with ceftaroline fosamil was shown to be noninferior to ceftriaxone (with or without clarithromycin) in the clinical cure rate at TOC in the 2 coprimary populations (Modified Intent-to-Treat Efficacy and Clinically Evaluable [CE]). Noninferiority was also demonstrated in the clinical response at End-of-Therapy (EOT) in the 2 coprimary populations. Finally, efficacy results consistently demonstrated similar cure rates between ceftaroline and ceftriaxone in important subgroups and key secondary analyses. Clinical response rates at Study Day 4 in these two studies were 69.6% and 69.0% for ceftaroline versus 58.3% and 61.4% for ceftriaxone.

4.3.Rationale for Present Study

Ceftaroline has excellent in vitro activity against *S.aureus* including MRSA, Group A streptococcus, *Streptococcus pneumoniae* and *Kingella kingae* which are the most common causes of acute hematogenous osteomyelitis in children. Ceftaroline is now approved by the FDA for treating children with community-acquired pneumonia and skin and soft tissue infections, conditions which are generally caused by the same bacteria that cause hematogenous osteomyelitis. Currently CA-MRSA is a major problem throughout the United States and the use of vancomycin or clindamycin has increased dramatically in children as a result.

Dosing of vancomycin is problematic and vancomycin has common side effects such as red man syndrome and renal dysfunction. Clindamycin is not recommended if there are concerns for concomitant bacteremia because it is a bacteriostatic agent. Daptomycin may be useful but is just being studied in pediatric patients for osteomyelitis and should not be used if there is evidence of concomitant pneumonia. Thus, the addition of another parenteral antibiotic for treatment of acute hematogenous osteomyelitis in children is desirable.

There is no safety data available for administering ceftaroline to adults every 8 hours. The safety data for administering ceftaroline every 8 hours to children has been determined in three pediatric trials. (Cannavino et al. A Randomized, Prospective Study of Pediatric Patients with Community-acquired Pneumonia Treated with Ceftaroline Versus Ceftriaxone. *Pediatr Infect Dis J* 2016; 35:752-9; Blumer et al. A Multicenter, Randomized, Observer-blinded, Active-Controlled Study Evaluating the Safety and Effectiveness of Ceftaroline Compared with Ceftriaxone Plus Vancomycin in Pediatric Patients with Complicated Community-acquired Bacterial Pneumonia. *Pediatr Infect Dis J* 2016; 35:760-6; Korczowski et al. A Multicenter, Randomized, Observer-blinded, Active-controlled Study to Evaluate the Safety and Efficacy of Ceftaroline Versus Comparator in Pediatric Patients with Acute Bacterial Skin and Skin Structure Infection. *Pediatr Infect Dis J* 2016; 35:e239-47. The most common adverse events for patients receiving ceftaroline were diarrhea and vomiting. Eosinophilia developed in about 5% of patients. The proportions of patients developing adverse events were similar for the

ceftaroline and comparator groups in each of these studies. We are using the same dose and interval for ceftaroline that was used for the pediatric trial of ceftaroline for complicated pneumonia (clinical trials identifier number NCT01669980).

4.4. Rationale for Ceftaroline Fosamil Dosage Regimen

The selected ceftaroline dose regimens (15 mg/kg [600 mg if > 40 kg] as a 2-hour infusion q8h) are expected to achieve PK/PD targets associated with 1-log kill of *S. aureus* in the murine pneumonia model for organisms with MIC values up to 1 mg/L in > 90% of patients 2 months to < 18 years. The median Cmax value in children 1 year to < 18 years with normal renal function dosed with 15 mg/kg q8h as a 2-hour infusion predicted to be less than the median Cmax value in adults dosed with 600 mg q8h as a 1-hour infusion. The median AUC0-24h in children 1 year to < 18 years dosed with the above regimen is predicted to be up to 15% greater than in adults dosed with 600 mg q8h. The median f T > MIC for an MIC of 1 mg/L is predicted to be 84-93% for the recommended pediatric dose regimens compared to 100% in adults dosed with 600 mg q8h.

Initially, the sponsor believed that a dose of 15 mg/kg q8h to match the dose of 600 mg q8h in adults was appropriate for children from 6 months to <18 years. However, based on findings in the pediatric ABSSI and CABP studies, a lower dose of 10 mg/kg q8h is more appropriate for children from 6 months to < 2 years in order to avoid higher AUC values. The 10 mg/kg q8h dose in this age range is expected to result in a median fT (unbound drug time over MIC) > MIC of 78-88% for an MIC of 1 mg/L and 58-66% for an MIC of 2 mg/L. This would give nearly 100% target attainment for a target of 50% at an MIC of 1 mg/L. The higher dose of 15 mg/kg q8h would still be appropriate for children 2 and older.

4.5. Outpatient Parenteral Antimicrobial Therapy

If a subject is going to require continued parenteral therapy with an antibiotic to complete therapy at home, they will be dropped from the study protocol because of the difficulty in providing parenteral antibiotics in a study using a home health company. Patient will continue therapy with another agent at home. The subjects will be followed and assessed for outcome at the time of discharge as well as for safety assessments at the completion of ceftaroline administration. The home therapy will be determined as clinically indicated for such subjects.

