6.2. Number of Subjects

18 Children 1 to 17 years of age, inclusive. Each subject will receive ceftaroline. 2 subjects above 5 years old will be enrolled before the younger subjects are enrolled.

Based on A'Hern's single-stage design for Phase II clinical trials 18 subjects would be required to reject $H_0: \pi \leq 0.50$ and conclude $H_1: \pi \geq 0.80$ with 80% power assuming a Type 1 error rate of 0.05.

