7.7. Subject Discontinuation or Withdrawal

Subjects should be encouraged to complete all study outcome assessments. However, a subject may be discontinued from study drug or may withdraw assent/consent to participate in this study at any time without penalty or loss of benefits to which the subject is otherwise entitled. Subjects will be assessed for safety of ceftaroline at the time points outlined in the schedule of evaluations, if possible.

7.7.1. Off Study Criteria:

- Subjects who require continued home parenteral antibiotics will be discontinued from the study.
- Subjects that require IV treatment after switching to Oral drug.
- If a subject's estimated CrCl decreases to < 50 mL/min during the treatment period, the subject will be discontinued from the study.
- Diarrhea (the occurrence of > 4 loose stools /day) with blood or mucus
- Moderate to severe maculopapular rash that does not resolve following administration of diphenhydramine (Benadryl®) or any urticarial rash.
- Absolute neutrophil count < 500 WBC/mm³ (Grade 4)
- Hemolytic anemia Grade 2 (evidence of > 2 g decrease in hemoglobin but does not require blood transfusion) or above.
- Thrombocytopenia-Platelet count < 100,000/mm³ (Grade 1)
- AST/ALT > 3 X ULN (grade 3)

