7.8. Premature Discontinuation From Study Drug Administration

7.8.1. Discontinuations Due to Safety

Assessments and Procedures: A subject who is prematurely discontinued from study drug administration (ie, before the anticipated full course of study drug required for effective treatment of hematogenous SA osteomyelitis *for safety reasons*) should have EOIV or EOT (if on PO drug) assessments conducted per Section 9, and undergo subsequent assessments at FU, if possible. The same procedures will be followed if the subject needs to continue home IV therapy to complete treatment because the subject is intolerant of an appropriate oral antibiotic or there is no oral agent that is active against the organism isolated.

Clinical Outcome Assessment:

If a subject prematurely discontinues the study drug due to an SAE and requires alternative non-study antimicrobials for hematogenous SA osteomyelitis, the subject should be assessed indeterminate.

Reasons: Reason(s) for premature discontinuation from study drug administration *due to safety* may include, but are not limited to, the following:

- Occurrence of an SAE that, in the opinion of the Investigator, warrants the subject's permanent discontinuation from the study drug or oral drug administration.
- Known pregnancy or breastfeeding during the drug administration period. A female subject whose pregnancy test is positive at the end of total treatment must be followed through the immediate postnatal period or until termination of the pregnancy. Every pregnancy will be reported as soon as possible (within 24 hours of learning of the pregnancy), as described in Section 11.1.4.

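### The sections on children who go home on IV therapy disagree about whether they stay in follow-up, so their end-of-therapy and one-year outcomes may not be collected

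*Combined protocol and SAP*

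**What the plan says.** Section 4.5 says of a child who will need parenteral therapy at home that "they will be dropped from the study protocol because of the difficulty in providing parenteral antibiotics" through a home health company. It then sets what is observed: "The subjects will be followed and assessed for outcome at the time of discharge as well as for safety assessments", the latter when ceftaroline is completed. No later visit is mentioned.

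The first off-study criterion in section 7.7.1 reads "Subjects who require continued home parenteral antibiotics will be discontinued from the study". It names no last visit.

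Section 7.8.1 describes children who stop study drug early for safety reasons. They get the end-of-IV (EOIV) assessments, or the EOT assessments if already on oral drug, and then the follow-up (FU) visit if possible. It goes on: "The same procedures will be followed if the subject needs to continue home IV therapy to complete treatment", but only where the child cannot tolerate a suitable oral antibiotic or no oral agent is active against the isolate. Section 9.7 places FU 12 months after the last dose. Clinical outcome, pathologic fracture and growth disturbance are assessed there.

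Other sections also bear on these children:
- Section 7.7 encourages completion of outcome assessments and provides for safety assessment at the scheduled time points, if possible.
- Section 7.8.2 covers stopping for insufficient therapeutic effect, including a change to another IV antibiotic.
- Section 7.8.3 codes a withdrawn child as indeterminate at later time points unless already a failure.
- Section 10.5 collects adverse events until EOT.
- Section 12.8 assesses data up to the time a child is dropped.

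**The concern.** Every one of these children has received ceftaroline, and section 7.9 replaces only children withdrawn before any dose. What happens to them afterwards is part of the result. Outcome at the end of total therapy and at one year are secondary objectives (5.2), and relapse or pathologic fracture within a year is a named outcome (6.1).

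Two staff members reading different sections could treat the same child differently. One would close the record at discharge. The other would book the 12-month visit. With 18 children, one or two such decisions move the one-year proportion visibly.

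The reason given in 4.5 is logistic: supplying study drug at home is difficult. That explains stopping ceftaroline. It does not explain stopping observation, since the child continues on another agent anyway.

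**Working it through.** **Step 1. The denominator.** Section 6.2 states "Based on A'Hern's single-stage design for Phase II clinical trials 18 subjects would be required" for a null rate of 0.50 and an alternative of 0.80, "with 80% power assuming a Type 1 error rate of 0.05". An exact one-sided binomial check takes, for each n, the smallest cutoff r with P(X ≥ r | n, 0.50) ≤ 0.05, and then the power P(X ≥ r | n, 0.80).

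| n | r | Type 1 error | Power |
|---|---|---|---|
| 16 | 12 | 0.0384 | 0.7982 |
| 17 | 13 | 0.0245 | 0.7582 |
| 18 | 13 | 0.0481 | 0.8671 |

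In a search over n = 8 to 25, 18 is the smallest n that meets both limits. The plan's figure is reproduced and is not in question. Section 6.2 states no allowance for lost outcomes.

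**Step 2. The sections side by side, by reason for going home on IV.**

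| Reason | 4.5 and 7.7.1 | Other section | Result |
|---|---|---|---|
| Oral intolerance, or no active oral agent | Off study; outcome at discharge, safety at end of ceftaroline (4.5) | 7.8.1: EOIV, then 12-month FU if possible | Direct contradiction over the one-year outcome |
| Insufficient therapeutic effect | Same | 7.8.2: EOIV (if on IV drug), safety at 4 to 6 weeks, failure at all later time points | Outcome settled; no explicit 12-month check for fracture or growth disturbance |
| Improving, but home IV for another reason | Same | None specific to this case | No EOT or 12-month outcome visit; may be indeterminate under 7.8.3 |

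**Step 3. Safety after discharge.** Section 4.5 stops at the end of ceftaroline. Section 7.7 refers to the scheduled time points, and 10.5 runs to EOT. All three cannot describe the same child. Section 7.8.1 does not settle it, because it gives the EOT assessments only to a child already on oral drug.

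**Step 4. Size.** The documents give no home-IV rate, so the number of exits k without a one-year outcome is an assumption. With s successes among the 18 − k observed children, the proportion in all 18 lies between s/18 and (s + k)/18, a width of k/18.

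- k = 1: 1/18 = 5.6 points
- k = 2: 2/18 = 11.1 points
- k = 3: 3/18 = 16.7 points

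Example: with k = 2 and 15 successes among the other 16, the range is 15/18 = 83.3% to 17/18 = 94.4%. If both exits were for insufficient effect, 7.8.2 makes them failures and the result is 15/18 with no range. The width therefore applies only to exits outside 7.8.2.

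**The case against.** The strongest reply is that the plan already follows most of these children. Section 7.8.2 gives exits for insufficient effect a later safety assessment and a definite outcome. Its listed reasons include worsening and lack of progress, and the list is open. Section 7.7 encourages outcome assessments in general, and 10.5 collects adverse events to EOT and follows unresolved ones further. Inclusion criterion 4 selects children expected to switch to oral therapy, so exits may be few.

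Most of this stands, and it limits the point. A reader might infer that slow responders vanish from the data and that the long-term results therefore rest on the easier cases. The documents do not support that: failures under 7.8.2 stay in the result. A reader might also infer that oral-phase safety is lost. A child never switched to oral drug has no oral phase; what is unsettled is safety between discharge and EOT.

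The reply does not remove the contradiction between 4.5 with 7.7.1 and 7.8.1. Nor does it give an outcome visit to the improving child who leaves for a reason outside 7.8.1 and 7.8.2. The general encouragement in 7.7 sits directly above a rule that takes that child off the study.

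**Conclusion.** The point holds as an inconsistency with a limited gap, and it should be corrected. For children going home on IV because of oral intolerance or lack of an active oral agent, the sections give opposite instructions on the 12-month visit. For improving children who leave for another reason, no EOT or 12-month outcome assessment is provided under 4.5 and 7.7.1.

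The effect falls on EOT and one-year outcome, relapse or fracture, and adverse events between discharge and EOT. The primary objective is not touched, because 4.5 and 7.8.1 both provide an assessment when ceftaroline ends.

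The size is 5.6 points of uncertainty per unobserved child, conditional on an exit count the documents do not state and on 18 treated children. A reader might turn this into a loss of power: if one child were missing, the exact figure would fall from 0.867 to 0.758. That would require the rate in section 6.2 to be a one-year success rate. Section 6.2 does not name its endpoint, so the verdict does not rest on power.

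**What to change.** Reconcile 4.5, 7.7, 7.7.1, 7.8.1, 7.8.2 and 10.5 into one rule. A child who leaves for home IV therapy, for any reason, is recorded as discontinued from study drug and not from the study. If the family agrees, the child is offered the scheduled EOIV assessment, an assessment at the time EOT would fall (Week 4 or Week 6 in section 9.6), and the 12-month visit. Adverse events are collected to the EOT-timed visit.

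Two details need wording. The EOT-timed visit should not depend on being on oral drug. The indeterminate code in 7.8.3 should apply to home-IV children only when the family declines or the child is lost. Failure scoring under 7.8.2 and the choice of home therapy stay as they are.

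The cost is a wording amendment and a few visits already in the schedule, for what is likely to be a small number of children. Some families may decline, so some outcomes may still be missing.

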4.6. Oral Drugs

A switch to one of the following open-label PO drugs (as per accepted clinical care processes) is expected / allowed on or after EOIV assessments are completed and if criteria in Section 9.2 are met:

- PO clindamycin 13 mg/kg/dose q8h in subjects with proven MRSA infection due to clindamycin susceptible MRSA or if no pathogen has been isolated.

OR

- PO cephalexin 25 to 33 mg/kg/dose q 8 hours in subjects with proven MSSA infection.

OR

- PO linezolid 600 mg q12h (Children > 12 years old) or 10 mg/kg q8h (children < 12 years old) in v5.0 (08Oct2018)

subjects with clindamycin-resistant MRSA pathogens or for subjects with MRSA isolates who are unable to tolerate clindamycin.

5. STUDY OBJECTIVES

5.1. Primary Objectives

- Evaluate the safety of ceftaroline in pediatric subjects 1 to 17 years of age (inclusive) with acute hematogenous osteomyelitis at the end of intravenous therapy.

5.2. Secondary Objectives

- Evaluate efficacy of ceftaroline in pediatric subjects with acute hematogenous osteomyelitis at the end of IV therapy, at the end of total therapy (anticipated to be at 4 to 6 weeks after enrollment), and at one year after enrollment.
- Evaluate clearance of *S. aureus* bacteremia if blood cultures initially positive.
- Assess proportion of patients with plasma levels of ceftaroline that exceed 1 µg/mL for over 60% of a dosing interval.

6. STUDY DESIGN

This is a Phase 1/2, open-label, single-center study to determine safety and tolerability of ceftaroline in pediatric subjects 1 to 17 years of age (inclusive) with signs and symptoms of acute hematogenous osteomyelitis at the end of intravenous therapy. After informed consent/assent is obtained, ceftaroline will be administered intravenously. After the subject has been afebrile for at least 48 hours, has negative blood cultures, is clearly improving in general, is able to eat and drink, and is able to use or move the involved extremity, the subject may be switched to oral antibiotic administration as outlined in section 5.4.2. The expenses will be covered by the study.

6.1. Outcome Measures

Primary: Safety evaluations will be conducted in the children who have started treatment with ceftaroline. Assessments will include:

- AEs, SAEs, deaths, and discontinuations due to SAEs.
- Vital signs and laboratory parameters.

Secondary:

- Clinical response (the subject has been afebrile for at least 48 hours, has negative blood cultures, is clearly improving in general, is able to eat and drink, and is able to use or move the involved extremity) at the end of parenteral therapy (approximately days 5 to 14) by subject and by baseline pathogens although *S. aureus* is expected to be the predominant pathogen.
- Clinical outcome (site of infection has complete resolution of pain, swelling and warmth and the patient is able to use the affected extremity normally and is back to normal activities) at the EOT and at the one year follow up visit.

- Clinical relapse within a year of enrollment in the study or the development of a pathologic fracture.

PK:

- Concentrations of ceftaroline fosamil, ceftaroline, and ceftaroline M-1 in plasma.
- If available, concentrations of ceftaroline fosamil, ceftaroline, and ceftaroline M-1 in purulent material such as bone or subperiosteal abscess or synovial fluid.

